We will partner with BroadReach Healthcare, a PEPFAR partner in South Africa, to pilot test an innovative index partner HIVSS strategy in one urban and one rural public health clinic in the Nkangala district of Mpumalanga Province to evaluate **acceptability, barriers, and preliminary efficacy** of secondary HIVSS distribution in a randomized control trial enrolling women newly diagnosed with HIV or on ART. In the intervention arm, women will receive counselling on how to use HIVSS, how to encourage their male partner to screen, and 2 HIVSSs with HIVSS instructions and invitation to return for confirmatory testing. In the standard of care arm, index women will receive counselling on the importance of disclosure to their family and partner(s) and referral for HIV testing (per SA national guidelines). We will evaluate the following aims:

1. Conduct a mixed-methods survey with N=100 HIV+ women to assess perceived **acceptability and barriers** (including perceived safety, IPV) to secondary HIVSS distribution by women to male partners.
2. Test the **feasibility** and **preliminary efficacy** of secondary HIVSS distribution through a 1:1 randomized control trial in n=100 HIV+ women to assess, comparing standard of care to intervention arm:
 - a. % of index women who self-report that they gave the HIVSS or standard of care referral for testing to their male partner
 - b. % of male partners who either screened or tested for HIV assessed at 3 months after randomization (*primary outcome*)
 - i. Measured via options of: index or partner self-report, SMS/WhatsApp of a picture of the used HIVSS sent by partner or index, return of a used self-test to the facility by either the index or partner, and/or partner coming into facility for with an invitation for confirmatory testing or SOC counseling referral
 - c. % of male partners with a positive HIV screening/test result
 - d. % of newly diagnosed male partners who initiate ART within 3 months of diagnosis
 - e. % of those on ART with viral suppression after 6 months on ART (index and partners)
3. In the intervention arm, we will assess acceptability and barriers (including safety/IPV) related to HIVSS distribution or use via surveys with all intervention participants who return for the study endline survey and a convenience samples of n=20 male partners (n=10 men who used HIVSS and n=10 men who did not use HIVSS)

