Baseline survey: After consent, a trained interviewer/counselor will administer a brief 10-15 minute survey to n=100 WLHIV about socio-demographics (age, education, relationship status), knowledge of partner's prior HIV testing and status, willingness to distribute HIVSS to their partner(s), facilitators/barriers to HIVSS (17). A trained study staff will ask the survey questions in the local dialect using RedCap. Participants will receive an option to participate in the interview on the phone instead of returning to the health facility.

Randomization: Following the baseline survey, women will be randomized to receive a HIVSS or referral in a 1:1 ratio to the intervention or standard of care arm. Randomization will be performed using a random number table by participant ID, who will be provided with sealed randomization envelopes. The participants will open the envelopes sequentially.

Male partner contact: For women allocated to the intervention arm, the participant will be given a HIVSS to take home to their partner(s). The counsellors will give the participant two options for contacting their partners:

- The participant will contact their partner (via a telephone call or SMS) while in the counselling session to confirm the partner's participation and obtain permission to provide his contact details.
- The participant will ask the partner to contact the counsellor to confirm participation and provide his contact details. If the participant confirms that her partner consented to participate in the study, the counsellor will call him to request his consent over the phone and confirm that he is her partner (using his name and date of birth). The interviewer will read the consent form on the phone and send him a copy via SMS/WhatsApp or email.

Standard of care arm: In the standard of care arm, women will receive standard of care partner referrals for HIV testing, including counselling about disclosure and referral for her partner(s) to return to the facility for testing. They will complete an endline survey after ~3 months (or when they return for their next clinical visit, ART start, or drug pick up visit) to evaluate the uptake of partner testing, results, and safety, including IPV.

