Female partner endline survey (intervention arm): Study staff in the facility will conduct a brief 10 minute endline survey in all participants who return at 3 months (or when they return for their next clinical visit, ART start, or drug pick up visit) to report on primary outcomes including partner HIV testing, results and confirmatory testing. If the women do not return in 3 months, UCT staff will conduct the survey telephonically.

Male partner endline survey (intervention arm): Following the survey and counselling, we will ask female participants to ask their partner if he consents (verbally or via SMS/WhatsApp) that we can follow them up. Study staff will contact women who agree in 24-48 hours following the survey to speak with her partner or ask her to give the study phone number to call us to consent to participate in a brief survey. We will attempt to recruit 20 male partners from the intervention arm (n=10 who used the test and n=10 who did not use the test) to provide informed consent to participate in study survey to evaluate use of HIVSS, acceptability (including linking HIVSS to couples testing or disclosure), barriers and any reported harms or reactions over the phone. Male partners will be asked about what they liked about HIVSS, acceptability and ease of use.

Note: All surveys will be translated into isiZulu and back-translated into English to confirm accuracy prior to implementation.

Human Resources: We will train 1-2 BroadReach and DoH HTS counsellors to select the women, consent them and interview them (30-45 minutes) and then either allocate the HIVSS or counselling about importance of partner testing, depending on randomization. A BroadReach Manager will manage the quality of the study and ensure a timely reporting, and contact colleagues at UCT with problems/queries. A trained UCT research staff will conduct the follow up surveys telephonically with women who are unable to return to the facility. The research staff will also conduct interviews with men (n=20) for the endline survey.

Table 1. Pilot study timeline

	Nov	Dec	Jan	Feb	Mar	Apr	May
Mpumalanga Province, District and UCT HREC proposal submission, review and approval	X						
Train HTS counsellors and BR manager in pilot study SOPs, survey and procedures	X						
Develop RedCap survey and pre-test with staff	X						
Recruit and enroll n=100 WLHIV in the study (n=50/month)			X	X			
Baseline survey and eligibility screening (n=100 WLHIV)			X	X			

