Randomize n=100 WLHIV to intervention vs standard of care			X	X			
Deliver HIVSS and instructions to n=50 and referral counseling to n=50			X	X			
Follow up participants at ~3 months (to coincide with next clinical visit) to conduct endline survey and evaluate HIV testing uptake, results					X	X	X

(positivity) and linkage (telephonically and using health records)						
Study endline survey for n=20 partners in the intervention arm (telephonically)				X	X	X
Analysis and dissemination					X	X

Evaluation: We will evaluate the following outcomes in the study including:

1. % of index women who self-report that they gave the HIVSS or SOC counseling referral to their male partner
2. % of male partners who either screened or tested for HIV assessed at 3 months after randomization (primary outcome)
 - i. Outcome measured via: index or partner self-report, SMS/WhatsApp of a picture of the used HIVSS sent by partner or index, return of a used self-test to the facility by either the index or partner, and/or partner coming into facility for with an invitation for confirmatory testing or SOC counseling referral
3. % of male partners with a positive HIV screening/test result (case finding)
4. % of newly diagnosed male partners who initiate ART within 3 months of diagnosis
5. % of those on ART with viral suppression after 6 months on ART (index and partners)

4. Ethical considerations

The study protocol, informed consent form, all data collection tools, and other requested documents will be reviewed and approved by the University of Cape Town Faculty of Health Sciences Human Research Ethics Committee (UCT-HREC).

Informed consent

The study informed consent for the study and questionnaire are modelled after that used in previous studies and will be delivered in participants' home language by trained interviewers. The informed consent form (ICF) will be translated into isiZulu and back-translated into English to confirm accuracy. This study ICF details the purpose of the study, study procedures, and the risks and benefits to women that participants may encounter at the second study visit. We will ask women if they want to consent to give her partners' contact information (phone number), but this will not be required to join the study.

Here, study staff will emphasize to participants that:

- Participation is entirely voluntary, and their choice regarding participation will in no way influence the quality of routine medical care for mothers

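### IPV after randomisation is to be collected in both arms, but the only aim that uses it is confined to the intervention arm and no between-arm comparison is stated

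*Combined protocol and SAP*

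**What the plan says.** Section 3, Study Objectives, Aim 2 is the only place that states a comparison of arms: a "1:1 randomized control trial in n=100 HIV+ women to assess, comparing standard of care to intervention arm". Its items a to e are kit or referral handed over, partner screened or tested (primary), partner positivity, ART initiation and viral suppression. The Evaluation list after Table 1 gives the same five, introduced by the word 'including'. IPV is in neither list.

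IPV after randomisation is the subject of Aim 3 only: "In the intervention arm, we will assess acceptability and barriers (including safety/IPV) related to HIVSS distribution or use via surveys with all intervention participants", if they come back at endline. Aim 1 mentions IPV in all 100 women, but as a perceived barrier. Its timing is not stated. It fits the baseline survey, which precedes randomisation.

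On data collection, the Standard of care arm paragraph says those women complete an endline survey at about 3 months "to evaluate the uptake of partner testing, results, and safety, including IPV". The Female partner endline survey (intervention arm) paragraph says women are "to report on primary outcomes including partner HIV testing, results and confirmatory testing", without naming IPV; Aim 3 supplies it. The follow-up row of Table 1 names testing uptake, results and linkage.

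The Safeguards paragraph in Section 4 provides an IPV risk screen at baseline and referral for support. It defines no endpoint and no analysis.

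**The concern.** IPV can occur in either arm. SOC women are counselled about disclosure, and the Risks list in Section 4 names partner violence following disclosure as a study risk. An IPV proportion from the intervention arm, read alone, could be taken as harm or as reassurance.

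Aim 3 also limits IPV to what relates to distributing or using the kits. That asks the respondent to judge cause, a judgement that a randomised comparison of any IPV does not need.

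The protocol gives IPV weight. The background supports the safety of secondary distribution with five randomised trials, and gives higher IPV levels as an example of how South Africa differs from Kenya and Malawi. The results are to be published and to inform a larger trial. With no comparison stated beforehand, it is open whether and how the SOC data will appear.

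**Working it through.** The plan gives no IPV rate, sample-size derivation or power figure to reproduce. The check is one of text, followed by an illustration of what a comparison would add and how precise it would be.

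**1. The text side by side**

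| Place | IPV after randomisation? | Arms |
|---|---|---|
| Aim 2, a to e | not named | both, compared |
| Evaluation list, 1 to 5 | not named | not specified |
| Aim 3 | yes, as a barrier related to the kits | intervention only |
| SOC endline survey | yes | SOC |
| Intervention endline survey paragraph | not named there; supplied by Aim 3 | intervention |

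Collection is planned in both arms. No aim or listed outcome brings the two together.

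**2. What the comparison adds**

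Inputs: 50 per arm (Section 3, Study design) with full follow-up assumed; all IPV counts are assumptions.

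Intervention arm alone, 10/50 = 20%, Clopper-Pearson 95% CI 10.0% to 33.7%.

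For the risk difference d = p1 - p2, Newcombe's interval uses each arm's Wilson limits (l, u):

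- lower = d - √[(p1 - l1)² + (u2 - p2)²]
- upper = d + √[(u1 - p1)² + (p2 - l2)²]

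For 10/50 v 5/50, the Wilson limits are 11.24% to 33.04% and 4.35% to 21.36%:

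- lower = 10 - √(8.76² + 11.36²) = 10 - 14.34 = -4.3
- upper = 10 + √(13.04² + 5.65²) = 10 + 14.21 = +24.2

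The same method gives:

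| Intervention | SOC | Difference, points (95% CI) |
|---|---|---|
| 10/50 | 5/50 | +10 (-4.3 to +24.2) |
| 10/50 | 10/50 | 0 (-15.7 to +15.7) |
| 10/50 | 15/50 | -10 (-26.3 to +7.0) |
| 10/50 | 3/50 | +14 (+0.5 to +27.6) |
| 5/50 | 0/50 | +10 (+0.9 to +21.4) |

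The first three rows share one intervention count and point in three directions. The last two exclude zero, so intervals that include zero are not inevitable.

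**3. Precision when the arms are equal (Newcombe half-width)**

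| Count in each arm | Half-width, points |
|---|---|
| 1/50 (2%) | 8.7 |
| 3/50 (6%) | 10.9 |
| 5/50 (10%) | 12.7 |
| 10/50 (20%) | 15.7 |
| 4/40 (10%, assuming 20% loss) | 14.4 |
| 8/40 (20%, assuming 20% loss) | 17.6 |

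**4. Power for a test, for context**

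Power = Φ{[|p1 - p2| - 1.96√(2p̄(1 - p̄)/n)] / √[(p1(1 - p1) + p2(1 - p2))/n]}.

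For 10% v 20%, n = 50: (0.10 - 1.96 × √0.0051) / √0.005 = (0.100 - 0.140)/0.0707 = -0.565, so power is about 29%. Fisher's exact test gives 19.5%. With 40 per arm the two figures are 24% and 16%. By the same formula with 50 per arm, power to detect a doubling is about 8% from 2%, 15% from 5% and 59% from 20%. The comparison can only be descriptive.

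**The case against.** The strongest reply is that a reference group exists: IPV is planned for collection in both arms, and what is missing is a statement that it will be compared. That stands. A reader might infer from Aim 3 that the trial has no control data on IPV. The SOC endline survey paragraph rules that out.

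A reader might also infer that the two arms are asked different things, because IPV is named in one endline paragraph and not in the other. The documents do not support this either. The intervention paragraph lists its content after 'including', Aim 3 places IPV in that survey, and the questionnaires are not in the text. No mismatch is shown; it cannot be judged. Nor does Aim 3's reference to women who return mean that the others go unasked: "If the women do not return in 3 months, UCT staff will conduct the survey telephonically".

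Aim 3 is also defensible for its own purpose, since only women given kits can report on their acceptability. The gap lies in Aim 2 and the Evaluation list, and the latter is not strictly closed. IPV is not neglected elsewhere: there is a baseline screen with referral, and the male partner survey asks about harms. None of these is a between-arm outcome.

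Finally, 100 women cannot support a firm conclusion. That is correct, but Aim 2 is about feasibility and preliminary efficacy, where estimates with intervals are the natural product.

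**Conclusion.** The concern holds as a gap in the stated outcomes and analysis. IPV after randomisation is collected in both arms, used by an aim in one arm only and there tied to the kits, and compared nowhere. The primary outcome is unaffected. The change is worth making because the risk is one that the protocol emphasises and the comparator data are already planned.

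A between-arm difference should not be read as the harm of the kits over background violence. SOC women receive disclosure and referral counselling, while the intervention is described as "women will receive counselling on how to use HIVSS, how to encourage their male partner to screen, and 2 HIVSSs". Whether intervention women also receive disclosure counselling is not settled in the text. The difference compares the two arms' packages, and equal rates could mean that both raise IPV.

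The size is illustrative. At assumed equal rates of 2% to 20% and 50 per arm, the 95% interval is about ±9 to ±16 points. With 20% loss it is about ±14 points at 10% and ±18 at 20%. No IPV rate or expected loss is given in the documents.

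**What to change.** Add any IPV since randomisation to the Aim 2 list and the Evaluation list as a descriptive safety outcome in both arms. Name it in the intervention endline survey paragraph, as is already done for SOC. Ask the same items over the same recall window in both arms, whether or not the woman links the event to the kits. Report the number asked, the proportion in each arm and the risk difference with a 95% CI. Keep Aim 3 for kit-specific acceptability and barriers.

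The cost is some outcome wording, a common set of IPV items and one table, with no extra participants or visits. The downside is the wide interval. The table should say that it compares the two arms' packages descriptively and that finding no difference is not evidence of safety.

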We will publish these results to inform PEPFAR index and HIVSS implementation in South Africa. This study will inform a larger trial to apply for a large research grant to the US National Institute of Health (NIH) in late 2021.

3. Study design

Randomized control trial of n=100 WLHIV (50 in each arm) in two facilities in the Nkangala district. We selected high-density facilities, Kwamhlanga CHC and Sr Mashiteng Clinic facility from a rural and urban area, respectively, to ensure that the results are generalizable. These facilities use oral HIV test kits, which has been shown to be more acceptable in terms of ease of use (20, 21). WLHIV will be recruited in antenatal care or in HIV care services. Inclusion criteria are listed below.

Inclusion Criteria:

1. Adult female 18+ years old
2. confirmed HIV-positive or on ART
3. confirmed to currently have a male partner and are sexually active
4. male partner is of HIV- or unknown status
5. confirmed to have a cell phone that can read and respond to SMS/WhatsApp messages
6. confirmed to be able to consent to study participation (no language constraints or psychological issues that would make it difficult to consent to participate in the study)

Exclusion criteria: Failure to meet all of inclusion criteria

Procedures for the informed consent process are outlined below. Throughout, trained BroadReach staff will ensure that women are aware of their right to refuse and/or withdraw from the study at any time. In addition, study staff will emphasize that all study activities are entirely separate from routine HIV care services received and that refusal or withdrawal from the study will have no impact on their ability to access any services provided at any public-sector health facility.

Study procedures

The study will be integrated into Kwamhlanga CHC (rural facility) and Sr Mashiteng Clinic facility (urban facility) in Nkangala district. WLHIV will be recruited directly from the clinic HCT, antenatal care, or ART services. All trained staff are already working in the facility part of the ongoing current APACE (Accelerating Programme Achievements to Control the Epidemic) programme under USAID. The trained study recruiter will recruit eligible directly from women in the study, and if interested and eligible after the screening process, the women will go to a private room for the study consent and interview.

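### One rural and one urban facility are chosen on purpose, but no facility-stratified primary estimate is stated; pre-specifying one is a cheap, low-priority gain in precision

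*Combined protocol and SAP*

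**What the plan says.** The Study Objectives place the trial "in one urban and one rural public health clinic in the Nkangala district of Mpumalanga Province". The Study design section gives the size, "Randomized control trial of n=100 WLHIV (50 in each arm) in two facilities in the Nkangala district", and explains the choice of sites: they come "from a rural and urban area, respectively, to ensure that the results are generalizable".

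On allocation, the Randomization paragraph under Study procedures sets a 1:1 ratio and states: "Randomization will be performed using a random number table by participant ID, who will be provided with sealed randomization envelopes". Envelopes are opened in sequence. The paragraph names no strata and does not say whether the two sites share one list or each has its own.

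On analysis, aim 2 describes a "randomized control trial in n=100 HIV+ women to assess, comparing standard of care to intervention arm". The Evaluation section lists the primary outcome as the percentage "of male partners who either screened or tested for HIV assessed at 3 months after randomization (primary outcome"). Neither place mentions facility, and neither names an effect measure, model or interval. Expected testing rates, enrolment per facility and any rural-urban difference in partner testing are not given.

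On use of the result, the Study Objectives say: "This study will inform a larger trial to apply for a large research grant".

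**The concern.** The sponsor treats rural or urban setting as important enough to fix by design, yet the planned comparison does not use it. If partner testing differs between the two facilities, part of the spread in the outcome is explained by facility. An unadjusted difference leaves that part in the error term, so it is less precise than the same 100 women allow.

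The structure of the envelope list decides how this shows. With a single list, the facility mix can differ between arms by chance and adds noise to the estimate. With balanced lists per facility, the mix is equal by construction. The usual unadjusted standard error ignores that balance and comes out too large when the facilities differ. In both cases the stake is precision, or a correctly sized standard error, in a pilot whose estimate is meant to inform a larger trial.

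**Working it through.** **Inputs from the documents:** 100 women, 50 per arm, two facilities, and a binary primary outcome at 3 months. There is no planned effect estimate to reproduce.

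**Assumed inputs:** 50 women per facility; partner testing of 60% (intervention) and 30% (standard of care), averaged over facilities; the same 30-point effect in both facilities; facility gap g of 0 to 40 points; no loss to follow-up; one partner per woman.

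**1. Facility mix under a single list.** With arm totals fixed at 50, the number k of rural women in one arm is Hypergeometric(100, 50, 50). The arms' rural shares differ by |2k − 50|/50. A gap of 10 points or more needs k ≤ 22 or k ≥ 28, which has probability 0.317. If arm totals are random (a separate 50:50 draw for each woman), the probability is 0.368. The fixed-total figure fits the stated 50 per arm better. With 30/70 enrolment by facility and fixed totals it is 0.275.

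**2. Variance by hand.** In each arm the facilities sit at p ± g/2, so the average within-facility variance is p(1 − p) − g²/4.

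- Unadjusted: (0.60×0.40 + 0.30×0.70)/50 = 0.45/50 = 0.0090, standard error 0.0949.
- Facility-stratified: (0.45 − g²/2)/50.
- Ratio: 0.45/(0.45 − g²/2).

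**3. Variance by simulation.** 200,000 trials per gap, single list, random arm totals, unadjusted against Mantel-Haenszel risk difference:

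| Facility gap | Ratio by hand | SE unadjusted | SE stratified | Simulated variance ratio |
|---|---|---|---|---|
| 0 | 1.000 | 0.0954 | 0.0958 | 0.99 |
| 10 | 0.45/0.445 = 1.011 | 0.0953 | 0.0953 | 1.00 |
| 20 | 0.45/0.430 = 1.047 | 0.0954 | 0.0937 | 1.04 |
| 30 | 0.45/0.405 = 1.111 | 0.0956 | 0.0911 | 1.10 |
| 40 | 0.45/0.370 = 1.216 | 0.0956 | 0.0870 | 1.21 |

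The simulated ratio is about 1% below the hand figure because stratification pays a little for uneven facility numbers between arms. Fixing arm totals gives almost the same ratios (0.989, 1.001, 1.036, 1.101, 1.205). The median 95% interval is about 37 points wide unadjusted, and 36.5, 35.4 and 33.8 points stratified at gaps of 20, 30 and 40.

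**4. Sensitivity (random arm totals).** With 30/70 enrolment by facility the ratios are 0.990, 0.997, 1.029, 1.078 and 1.162. With rates of 75% and 35% they are 1.039 at a 20-point gap and 1.226 at 40. With 50% and 25% they are 1.037 and 1.211.

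**5. Validity.** The mean error of either estimate is below 0.001. Coverage of the unadjusted 95% interval is about 94% at every gap.

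**6. Balanced lists per facility.** With 25 women per arm in each facility the two point estimates coincide. At a 40-point gap the true standard error is √(0.37/50) = 0.086, while the usual unadjusted standard error averages 0.094. The stratified analysis removes this mismatch.

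**The case against.** The strongest reply is that the benefit depends on a quantity the documents do not give. At gaps of 0 to 10 points there is nothing to gain, and at 20 points a 37-point interval shrinks by about half a point. Only at 30 to 40 points is the gain useful. Both clinics are in one district, both are described as high-density and both use oral kits, so nothing in the text points to a gap that large. This stands, and it is why the point has low priority. It does not remove the point, because the cost of adjusting when facility does not matter is about 1% of variance.

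A second reply is that the plan names no effect measure or analysis method at all, so facility is one clause of a larger omission. That is fair. If the primary analysis is being written anyway, this belongs in the same sentence.

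Two stronger readings are tempting. A reader might infer that the facility mix is left to chance. The documents do not say so: they are silent on list structure, and with two physical sites separate envelope sets are possible. A reader might also infer that the comparison is biased or its interval invalid. It is not: randomization keeps the unadjusted difference unbiased, and the interval already allows for chance imbalance.

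**Conclusion.** The point holds as a modest improvement in precision, not as an error in the design. The plan chooses its two facilities for their rural and urban settings but states no estimate that uses facility, and does not say how the envelope list is organised.

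Under the assumptions above, a facility-stratified estimate changes variance by about −1% to +1% at gaps of up to 10 points. The unadjusted variance exceeds the stratified one by about 4% at 20 points, 10% at 30 and 21% at 40. At the top of that range the gain is what about 21 more women would bring (100 × 1.21 = 121). If the lists were in fact balanced per facility, the case for stratifying is a correctly sized standard error. These sizes assume a common effect in both facilities, complete follow-up and one partner per woman. The plan itself allows for women who do not return and for more than one partner, so they are illustrations, not forecasts. Severity: consider.

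**What to change.** Add one or two sentences to the Evaluation section. Pre-specify the primary comparison as the Mantel-Haenszel risk difference stratified by facility, with a 95% interval, and report the unadjusted difference alongside. Fix this before outcomes are seen, so that the choice between the two estimates cannot depend on the results.

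Add one sentence to the Randomization paragraph saying whether the envelope list is single or per facility. No change to the allocation procedure is proposed.

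Each woman's facility is already known, so no participants, visits, staff or data are added. The only statistical cost is about 1% more variance if facility turns out not to matter.

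### The endline that supplies the 3-month primary outcome can be held at any earlier routine visit, and Table 1 opens endlines in March, before any woman has 90 days of follow-up

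*Combined protocol and SAP*

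**What the plan says.** The Study Objectives and the Evaluation list give the primary outcome a fixed time point. In the Evaluation list it is the percentage "of male partners who either screened or tested for HIV assessed at 3 months after randomization (primary outcome").

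The survey that reports it has a looser time point:

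- **Intervention arm** (Female partner endline survey): the survey is for participants who "return at 3 months (or when they return for their next clinical visit, ART start, or drug pick up visit").
- **Standard of care arm:** women complete an "endline survey after ~3 months (or when they return for their next clinical visit, ART start, or drug pick up visit").

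The intervention-arm paragraph adds that UCT staff will telephone women who have not returned by 3 months. No section gives an earliest day or a visit window.

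Table 1 places enrolment ("Recruit and enroll n=100 WLHIV in the study (n=50/month")) and randomization ("Randomize n=100 WLHIV to intervention vs standard of care") in January and February. Its follow-up row is marked for March, April and May. It reads "Follow up participants at ~3 months (to coincide with next clinical visit) to conduct endline survey and evaluate HIV testing uptake, results" and continues "positivity) and linkage (telephonically and using health records").

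The Evaluation list also allows the outcome to come from kit photographs, returned kits or the partner attending the facility. It gives no cut-off day for any source.

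**The concern.** The outcome is defined at 3 months, but its main data collection may be triggered by the woman's own care schedule. Women are recruited from HIV testing, antenatal and ART services, and nothing in the protocol shows that these services share a return interval. A woman due back in a few weeks could complete her endline then. A test her partner takes later, but still within 3 months, could be missed.

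The reported proportion would then average over unequal follow-up, some of it short. Identical wording in the two arms does not guarantee a fair contrast, because a short cut-off distorts the difference if partners test at different speeds by arm. The standard of care endline also collects safety information, including intimate partner violence, so an early survey shortens that observation as well.

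The pilot is meant to inform a larger trial. A proportion with no defined follow-up is a weak planning figure.

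**Working it through.** The plan states no figure for follow-up at endline, so there is none to reproduce. The check is calendar arithmetic.

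**Inputs from Table 1.** 50 women are randomized in January and 50 in February; endlines are in March to May.

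**Assumptions.** Enrolment is even within each month: 50/31 per day in January and 50/28 per day in February. February has 28 days, inferred from the August 2020 programme data and the late-2021 grant plan; a 29-day February changes follow-up by at most one day.

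**Step 1: range of follow-up.** Follow-up is the reference date minus the randomization date, from the last woman (28 February) to the first (1 January).

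| Date | Shortest (days) | Longest (days) |
|---|---|---|
| 1 March | 1 | 59 |
| 31 March | 31 | 89 |
| 30 April | 61 | 119 |
| 31 May | 92 | 150 |

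**Step 2: when the first woman reaches each mark.** 1 January + 75 days = 17 March; + 84 days = 26 March; + 90 days = 1 April.

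**Step 3: women of 100 with enough follow-up.** The number is the days of enrolment early enough, times the daily rate.

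| At least | By 31 March | By 30 April | By 31 May |
|---|---|---|---|
| 75 days | 15/31 × 50 = 24.2 | 50 + 14/28 × 50 = 75.0 | 100 |
| 84 days | 6/31 × 50 = 9.7 | 50 + 5/28 × 50 = 58.9 | 100 |
| 90 days | 0 | 30/31 × 50 = 48.4 | 100 |

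These are counts of women who have accrued the follow-up, not counts of early surveys.

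**Step 4: can the effect on the contrast be signed?** The protocol gives no testing rates or times to test, so this step is an illustration on assumed values only. Suppose 75% and 40% of partners test by day 91, a true difference of 35 points. Let the proportion tested by day t be F(t) = p × (1 − exp(−t/τ)) / (1 − exp(−91/τ)). With every endline at day 28:

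- τ = 14 days (intervention) and 45 days (standard of care): 64.9% against 21.4%, about 44 points.
- τ = 14 days in both arms: 64.9% against 34.6%, about 30 points.
- τ = 30 days in both arms: 47.8% against 25.5%, about 22 points.

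The difference can be overstated or understated, so no direction is claimed.

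**The case against.** The strongest reply is that the intent is clear. The outcome is fixed at 3 months in two places, Table 1 speaks of about 3 months combined with a routine visit, and the telephone rule uses the same anchor. On that reading the bracketed alternative means a routine visit near 3 months. This is a fair account of intent, but the *or* in both arm descriptions does not require it. The telephone rule guards only against late surveys, and a March opening does not fit the mild reading for most women.

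Second, the Table 1 row is composite and monthly. A March mark could stand for record review, and the first woman misses 90 days in March by one day. Table 1 is also only indicative, since it ends before 6-month viral suppression could be measured. These points weaken any inference about exact days. Still, conducting the endline survey is the first purpose the row names, and even at 75 days only about a quarter of women qualify by the end of March.

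Third, other sources could capture later tests, and Table 1 provides telephone and health-record follow-up. But no text says that capture continues to 3 months after an early survey, or that the woman is contacted again.

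Fourth, no harm is quantified, the rule is essentially the same in both arms, and this is a pilot. All of that is true. It limits what can be said about bias, but it does not turn a mixed follow-up into a 3-month proportion.

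**Conclusion.** The concern holds and should be fixed. The rule for the endline permits follow-up shorter than the time point of the primary outcome, in both arms and with no minimum. Table 1 opens that endline in a month when no woman reaches 90 days and, at its close, about 10 of 100 have reached 84 days and about 24 have reached 75.

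The conflict in the text is certain. The counts rest on even enrolment and a 28-day February. How many endlines would be early, and the direction and size of any bias between arms, remain unknown because visit intervals and time to test are not given.

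**What to change.** In both arms:

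1. Define the primary outcome as partner screening or testing dated within 90 days of randomization, from any listed source.
2. Record the test date in RedCap.
3. Treat earlier clinic, ART-initiation or medicine-collection visits as interim contacts that do not close the outcome.
4. Hold the endline on or after day 90 within one stated window, by telephone if no visit falls in it.
5. In Table 1, start endlines in April. The last day-90 date is 28 February + 90 days = 29 May, so any window longer than 2 days needs June.

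**Cost.** The changes are protocol wording, one date field and repeat surveys for women seen early. The intervention-arm survey is described as a "brief 10 minute endline survey". Assuming the same length in the standard of care arm, the most it could take is 100 × 10 = 1,000 minutes, about 17 hours, before call attempts and tracing. UCT staff already have the telephone role for women who cannot return, and it would be extended to those seen early. Some test dates will rest on the woman's recall, and a second contact adds some burden.

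A +7-day window ends on 5 June and runs past May for 5/28 × 50 = 8.9, about 9 women. A +14-day window ends on 12 June and does so for 12/28 × 50 = 21.4, about 21 women. Final analysis waits for those endlines.
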